***Consideration for possible pseudoprogression / treatment-related effect**

Immunotherapy may be associated with transient inflammatory-mediated increase in tumor size, or “pseudoprogression.” In many cases, it may not be initially possible to distinguish true progression from pseudoprogression.

Where pseudoprogression is suspected in a patient who meets criteria for PD, the patient may continue on study therapy. A shorter interval repeat MRI may be performed if clinically indicated but is not required. Corticosteroids may be considered for symptomatic patients. See section 9.5 for additional information regarding visual symptoms due to suspected pseudoprogression.

If the tumor size is stable or smaller on repeat imaging, and any signs and symptoms related to progression vs pseudoprogression are stable or have improved, patient may remain on study and continue protocol therapy. If the repeat MRI shows continued disease progression, then patient will be permanently removed from therapy and the time of progression will be the date of the initial MRI showing progression.

10.5. Duration of Response

Duration of overall response: The duration of overall response is measured from the time measurement criteria are met for CR or PR (whichever is first recorded) until the first date that recurrence or PD is objectively documented, taking as reference for PD the smallest measurements recorded since the treatment started.

Duration of overall complete response: The duration of overall CR is measured from the time measurement criteria are first met for CR until the first date that recurrent disease is objectively documented.

Duration of stable disease: Stable disease is measured from the start of the treatment until the criteria for progression are met, taking as reference the smallest measurements recorded since the treatment started.

Progression-Free and Overall Survival: Progression-Free Survival (PFS) is defined as the duration of time from patient enrollment to time of objective disease progression or death from any cause.

Overall Survival (OS): Overall survival is defined as the duration of time from patient enrollment to time of death from any cause.

10.6. Central Review

Central imaging review for response evaluation will be performed at the conclusion of the trial. Optional imaging studies will also be reviewed. Real time response determination will be made by the site investigator based on the local MRI read. For assistance with response determinations, a real-time MRI review may be requested in consultation with the study chair. In addition to the primary RAPNO response determinations, response assessments will also be made using RANO criteria. RANO response assessments will be used to satisfy the exploratory response comparison objective only, and will not be used for the primary response determination. RANO criteria are as described by Wen et al.⁵⁶

10.7. Ophthalmologic (Visual Acuity) Response Criteria

See section 9.5 regarding visual response criteria.

See “Consideration for possible pseudoprogression/treatment-related effect” in section 10.4 regarding management of pseudoprogression.

11. ADVERSE REPORTING REQUIREMENTS

11.1. Definitions

Adverse Events: An adverse event is any new, undesirable medical occurrence or change (worsening) of an existing condition in a participant that occurs from study enrollment until 30 days after drug discontinuation, whether or not considered to be product related. Therefore, adverse events are treatment emergent signs or symptoms. Elective hospitalizations for pretreatment conditions (e.g., elective cosmetic procedures) are not adverse events. Non-clinically significant abnormal laboratory values should not be reported as adverse events; however, any clinical consequences of the abnormality should be reported as adverse events. All adverse events must be noted on the electronic case report forms and submitted via eDCS within 2 weeks of completion of every treatment cycle.

For all adverse events, the investigator must pursue and obtain information adequate both to determine the outcome of the adverse event and to assess whether it meets the criteria for classification as a serious adverse event requiring immediate notification (within 24 hours) to the site PI and clinical coordinator, as well as the NFCTC Operations Center. Follow-up of the adverse event, even after the date of therapy discontinuation, is required if the adverse event or its sequelae persist. Follow-up is required until the event or its sequelae resolve or stabilize at a level acceptable to the investigator and sponsor.

Serious Adverse Events: A serious adverse event is defined by regulatory agencies as one that suggests a significant hazard or side effect, regardless of the investigator's or sponsor's opinion on the relationship to investigational product.

This includes, but may not be limited to, any event that (at any dose):
is FATAL;
is LIFE THREATENING (places the participant at immediate risk of death);
requires HOSPITALIZATION or prolongation of existing hospitalization;
is a persistent or significant DISABILITY/INCAPACITY; or
is a CONGENITAL ANOMALY/BIRTH DEFECT

Important medical events that may not be immediately life threatening or result in death or hospitalization but may jeopardize the participant or require intervention to prevent one of the outcomes listed above, or result in urgent investigation, may be considered serious. Examples include allergic bronchospasm, convulsions, and blood dyscrasias.

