6.4. Dose Modifications for Toxicity

Dose modifications below apply to toxicities that are at least possibly related to study drug. Laboratory results requiring drug hold must be repeated weekly or sooner if clinically indicated until they meet the criteria for restarting drug.

Liver Toxicity

If AST/ALT > 5x ULN while on study, poly-ICLC will be held until the AST/ALT \leq 5x ULN; if resolved within 21 days, maintain the dose 20 mcg/kg/dose twice weekly.

If event resolves >22-28 days, hold study drug until values < 2.5x ULN then restart at the reduced dose of 10 mcg/kg/dose twice weekly.

If AST/ALT do not decrease to \leq 5x ULN within 28 days (despite holding the drug for 28 days and only if elevated AST/ALT is attributable to the drug), then the study drug will be stopped, and participant will be off treatment for toxicity.

It is recommended to evaluate other medications that participant is taking for potential liver toxicity (e.g. acetaminophen, trimethoprim/sulfamethoxazole, seizure medications). It is also recommended to evaluate potential viral liver infection if there is persistent elevation of AST/ALT.

Elevations of AST/ALT are expected, and repeat elevations do not require permanent drug discontinuation unless deemed medically necessary by the treating physician after discussion with the principal investigator.

Hematological Toxicities: Thrombocytopenia

Continue drug at 20 mcg/kg/dose unless platelet count is less than 75,000/mm³. Then refer to the table below for further instructions.

Platelet (Plt) < 75,000/mm ³	Interrupt study drug until Plt \geq 75,000/mm ³ . If the event resolves within 21 days, then study drug may be restarted at the same dose. If Plt count of <75,000/mm ³ attributable to the study drug, and the event resolves between 22-28 days, then study drug may be restarted at lower dose of 10 mcg/kg/dose. If Plt is <75,000/mm ³ after 28 days and at least "possibly" attributed to study drug, the participant will be taken off protocol therapy. Transient and repeated thrombocytopenia is expected and does not require permanent removal from study therapy unless deemed medically necessary by the treating physician after discussion with the principal investigator or study team.
---	---

Hematological Toxicities: Neutropenia

Continue drug same dose until absolute neutrophil count (ANC) is less than 750/mm³, then refer to the table below for further instructions.

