11.2. Grading of Adverse Events using Common Terminology Criteria (CTCAE)

Adverse events (toxicities) will be graded according to the National Cancer Institute CTCAE version 5.0 for reporting of adverse events. A copy of the current version of the CTCAE version 5.0 can be downloaded from the CTEP home page:

https://ctep.cancer.gov/protocolDevelopment/electronic_applications/ctc.htm

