11.4. Reporting Procedures for All Adverse Events

All observed or volunteered adverse events, regardless of suspected causal relationship to study drug, will be recorded as Adverse Events in the electronic case report forms and submitted via eDCS within 14 days of completion of each treatment cycle. Events involving adverse drug reactions, illnesses with onset during the study, or exacerbation of pre-existing illnesses should be recorded. Objective test findings (e.g. abnormal laboratory test results) should also be recorded if considered to be clinically significant by the treating investigator.

It will be left to the investigator's clinical judgment whether or not an adverse event is of sufficient severity to require that the participant should be removed from treatment. A participant may also voluntarily withdraw from treatment due to what he or she perceives as an intolerable adverse

event. If either of these occurs, the participant will be given appropriate care under medical supervision until symptoms cease or until the condition becomes stable.

The severity of toxicities will be graded in accordance with the Common Terminology Criteria for Adverse Event (CTCAE) version 5.0 ([CTCAE v5 Quick Reference](#)).

The relationship of adverse events to the study medications will be assessed by means of the question: "Is there a reasonable possibility that the event may have been caused by the study medication?", Please answer Yes or No.

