- Progression free survival (PFS), defined as the time from start of treatment to the first occurrence of tumor recurrence, tumor progression, occurrence of a second malignancy, or death from any cause. Patients event-free at last follow-up will be censored in analysis. PFS will be determined at 12, 24 and 60 months.
- Objective response rate (defined as CR or PR) after 24 cycles of treatment. Response will be assessed through the time of the post-24th cycle tumor assessment, or through the last tumor assessment time during this nominal period for patients in follow-up, but who have withdrawn from protocol therapy, or through the last available tumor assessment for patients who are lost to follow-up during this time.
- Clinical benefit defined as (CR+PR+MR+SD). Clinical benefit will be assessed through the time of the post-12 and 24th cycle tumor assessment, or through the last tumor assessment time during this nominal period for patients in follow-up but who have withdrawn from protocol therapy, or through the last available tumor assessment for patients who are lost to follow-up during this time.
- The grade and duration of CTCAE toxicities observed during treatment using CTAE version 5.0.
- Evaluation for visual acuity for patients with optic pathways gliomas will be assessed at 12 months and 24 months from starting therapy. Patient visual outcome will be assessed through the time of the post-12th and 24th cycle visual assessment, or through the last visual assessment time during this nominal period for patients in follow-up but who have withdrawn from protocol therapy, or through the last available tumor assessment for patients who are lost to follow-up during this time.

Exploratory Endpoint

The RANO criteria for response assessment will be determined and descriptively compared to the primary response using RAPNO.

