14.3. Statistical Analysis Plan

The primary goal of the study is to evaluate the effectiveness of the poly-ICLC. Based on the single stage design, response of the drug will be determined after 16 participants are evaluable for the primary endpoint assessment. Participants will be classified based on response (CR/PR vs. MR/SD/PD). If at least 3 of 16 participants respond to treatment, the hypothesis that $P \leq 5\%$ is rejected at alpha = 0.05 and accept that the higher rate of P greater or equal to 25% is more likely; otherwise, the drug will be deemed ineffective based on having an objective response rate

not significantly different than the objective response rate of a poor drug. Comparison between RANO and RAPNO response criteria will be descriptive only.

Key secondary outcomes will be examined at baseline including clinical, quality of life and visual function. Following complete accrual, study enrollment and completion will be summarized as per a Consort Diagram with reasons for withdrawal or unable to complete the study. Appropriate data analysis sets will be defined as follows. The full-analysis set will include data from all participants who receive ≥ 1 dose of therapy on this study; a safety analysis set will comprise data from participants in the full-analysis set with any treatment doses. Other data sets (responding, evaluable) will be defined and will include data from participants who have the necessary baseline and on-study measurements to provide interpretable results for specific parameters of interest.

Descriptive summaries will be prepared to show sample size, mean, standard deviation, 95% confidence intervals (CIs) median, minimum, and maximum for continuous variables and counts, percentages, and 95% CIs for categorical variables.

For endpoints relating to tumor control, participant well-being, and biomarkers, analyses will be done based on the full analysis, responding, evaluable data sets, as appropriate. Time-to-event analyses will be performed with reference to the date of first treatment on this study. Analyses will focus on evaluation of outcomes and will be largely descriptive. Changes in tumor volumes will be summarized by medians, ranges, and the corresponding 95% CI.

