Based on the safety analysis set, information regarding study treatment administration, drug dosing and cycle compliance, safety variables, will be described and summarized. Data from the biological analysis will also be described and summarized. Safety will be assessed via tabulations of AEs and SAEs as well as Diary recordings following treatment dose/cycle of therapy.

All analyses for outcome results will be based on evaluable participants, as defined in section 14.

At the end of the trial, we will report poor performance if the treatment is rejected when not meeting the criteria of at least 3 responders' cases. If there is no success, we will report a failure to reject the null hypothesis. If the null hypothesis is rejected, the probability of the estimated success rate will be reported and 95% confidence intervals as well as the distribution of changes in tumor size.

Dose-limiting toxicity (DLT) is not an objective in this trial. Toxicity will be continuously monitored.

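### The CTCAE toxicity endpoint takes in laboratory abnormalities only when the investigator judges them clinically significant; grading the scheduled CBC and CMP values as well would be a cheap improvement (minor)

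*Combined protocol and SAP*

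**What the plan says.** Section 14 lists this secondary endpoint: "The grade and duration of CTCAE toxicities observed during treatment using CTAE version 5.0". Section 11.2 says what is graded: "Adverse events (toxicities) will be graded according to the National Cancer Institute CTCAE version 5.0 for reporting of adverse events". Grading is therefore tied to adverse events.

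Two sections decide when a laboratory result becomes an adverse event. Section 11.1: "Non-clinically significant abnormal laboratory values should not be reported as adverse events". The same sentence goes on to require that any clinical consequences be reported. Section 11.4 names who decides: "Objective test findings (e.g. abnormal laboratory test results) should also be recorded if considered to be clinically significant by the treating investigator".

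For the analysis, Section 14.3 says: "Safety will be assessed via tabulations of AEs and SAEs as well as Diary recordings following treatment dose/cycle of therapy". A separate sentence promises, for the safety set, that "information regarding study treatment administration, drug dosing and cycle compliance, safety variables, will be described and summarized", but it does not say what the safety variables are. The general reporting format is summary statistics for continuous variables and "counts, percentages, and 95% CIs for categorical variables".

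Blood is drawn on a fixed schedule in any case (Section 5.2, Appendix 3), and Section 13.4 requires data from each required evaluation to go into eDCS within two weeks.

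**The concern.** An endpoint defined by CTCAE grade suggests that laboratory toxicity will be graded from the measured values. As written, the only specified route from a CBC or CMP result to the endpoint runs through the investigator's opinion of clinical significance. That filter works in one direction: it can remove laboratory events from the table and cannot add any. Two sites can also treat the same value differently.

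Section 2.1 motivates the trial by the need for effective treatments with minimal side effects, so a table that leans towards fewer laboratory toxicities leans towards that claim. What is at stake is the accuracy of a descriptive secondary result in up to 20 participants.

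**Working it through.** **1. Route to the endpoint.** A result is drawn (5.2); the investigator judges its significance (11.1, 11.4); if significant, it becomes an adverse event and is graded (11.2); adverse events are tabulated (14.3) and supply the Section 14 endpoint. Section 5.2 and Appendix 3 also require toxicity review at treatment visits, but that review feeds adverse event forms subject to the same filter. No section says that laboratory values that are not adverse events will be graded.

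**2. Where the gap lies.**

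| Analyte | Value-based rule (4.2.1, 6.4) | What can go unrecorded |
|---|---|---|
| AST, ALT | held above 5 x ULN | elevations up to 5 x ULN |
| ANC | held below 750/mm³ | reductions to 750 or more |
| Platelets | held below 75,000/mm³ | reductions to 75,000 or more |
| Hemoglobin | 8.0 g/dL or more to start a cycle | reductions to 8.0 or more |
| White cells, lymphocytes, bilirubin, creatinine | none named | any asymptomatic change not judged significant |

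A value that stops the drug is very likely to be called clinically significant; this is an inference, since no section says that a hold is automatically an adverse event. Analytes in the last row meet a dose rule only through the 6.4 table for all other adverse events, so they must be recorded as adverse events first.

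**3. Do the documents show that sub-hold change is common at this dose?** They do not.
- Section 6.4 says "Elevations of AST/ALT are expected, and repeat elevations do not require permanent drug discontinuation unless deemed medically necessary", with similar wording for platelets and neutrophils. Each statement sits inside a hold-level rule and concerns whether repeats require permanent discontinuation.
- Section 6.6 describes mild, usually transient enzyme elevation with intravenous doses of 20 to 100 mcg/kg, and transient leukopenia at higher doses. Section 6.1 ties enzyme elevation to higher intravenous doses and calls leukopenia rare. This trial gives 20 mcg/kg intramuscularly.
- Section 2.3 reports grade 3 leukopenia in 1 of 4 children with low-grade glioma. That event was not mild, and it was recorded. The exact (Clopper-Pearson) 95% interval for 1/4 is 0.6% to 80.6%, too wide to project.
- Section 2.4, on the earlier pediatric phase II trial, was not in the text I had, so any rate given there is not reflected here.

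**4. Direction, with assumed inputs.** The plan gives no figure to reproduce. Let π be the share of 20 participants with a sub-hold abnormality and c the share of those that investigators call significant. Participants in the table = 20 x π x c.

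| π (assumed) | Affected, 20 x π | Recorded at c = 75% / 50% / 25% (assumed) |
|---|---|---|
| 20% | 4 | 3 / 2 / 1 |
| 40% | 8 | 6 / 4 / 2 |
| 60% | 12 | 9 / 6 / 3 |

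Neither π nor c is in the documents. The table shows only that the count depends on judgment; it does not estimate the loss.

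**5. What is already drawn.** For a participant who completes 24 cycles:
- CBC after baseline: cycle 1 day 8, cycle 1 day 15, day 1 of cycles 2 to 24, end of therapy = 1 + 1 + 23 + 1 = 26.
- CMP after baseline: day 1 of cycles 2 to 24, end of therapy = 23 + 1 = 24.

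**6. What those draws can resolve.** After cycle 1 they are about 28 days apart; with the ±5-day window on each, 28 − 10 = 18 to 28 + 10 = 38 days. On a 28-day grid an episode shorter than 28 days meets at most one draw. The time from first abnormal to first normal draw then reads 28 days whatever the true length. Worst grade and shift are usable; duration is not.

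**The case against.** Keeping non-significant laboratory values off adverse event forms is normal practice and not an error. Clinical consequences are still reported. Section 14.3 already promises a summary of safety variables, separately from the adverse event tabulation, and Section 13.4 suggests that the values may be in eDCS, so a graded table could be produced later. The endpoint is descriptive, most toxicities in Section 6.6 are clinical, and low-grade shifts in a small single-arm trial say little about causation.

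Most of this stands, and it is why the point is minor and the adverse event filter should stay. What remains is that the term safety variables is undefined, and nothing says laboratory values will be graded by CTCAE although the endpoint is a CTCAE grade. Section 13.4 does not say that numeric results are entered.

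A reader might go further and infer that mild hepatic and blood-count changes are expected in this trial and will be missed in quantity. The sources in step 3 of the working do not support that. A reader might also infer that participants are left unprotected. The holds for AST/ALT, ANC and platelets, and the cycle-start criteria including hemoglobin, act on the values themselves, whatever is written on the adverse event form.

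**Conclusion.** The point holds as a cheap improvement of minor severity. Asymptomatic hepatic and blood-count changes below the hold levels can be under-counted in the toxicity endpoint and can vary by site. The size cannot be derived from the documents, and they do not establish how often such changes occur at this dose and route. The conclusion rests on two readings: that the undefined safety variables do not already include CTCAE-graded laboratory values, and that values at hold level are in practice recorded as adverse events. The rule of 3 responders in 16, its alpha and its power are untouched.

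**What to change.** In Section 14.3, state that safety variables include AST, ALT, bilirubin, creatinine, hemoglobin, white cells, ANC, lymphocytes and platelets from the scheduled CBC and CMP draws, graded by CTCAE v5.0 in the safety set regardless of clinical significance. Beside the adverse event table, report worst post-baseline grade and a shift table from baseline grade.

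Label both as all-cause. The Section 3.1 entry limits for AST/ALT, ANC and platelets equal the hold limits, and myelosuppressive chemotherapy is allowed up to 4 weeks before registration, so some abnormalities will be pre-existing or carried over. Leave the adverse event form rule as it is, and do not derive laboratory-based duration from the roughly monthly draws.

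The cost is plan wording and programming; if numeric results are not already in eDCS, entry of up to 26 CBCs and 24 CMPs per participant after baseline, plus the baseline values; and laboratory toxicity rates that may look slightly less favourable. No new blood tests or visits are needed.
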